SimCapture, developed by the Norwegian medical education company Laerdal (well known for the "Resusci Anne" manikin and emergency simulation scenarios), is an advanced medical education management platform that integrates audio, video, annotations, patient monitor data, and simulator outputs into a unified web interface.

As a mobile learning technology, SimCapture enables students to record their practice sessions, upload the videos to a cloud platform, and receive targeted instructor feedback alongside peer performance reviews (15, 16). By facilitating visual and interactive learning, SimCapture aligns closely with the principles of observational learning, enabling students to model correct procedures, self-reflect, and progressively improve their clinical skills and confidence.

2. Research Theme and Objectives

The purpose of this study is to design a SimCapture-based instructional approach grounded in the theory of observational learning, in order to enhance nursing students' performance in clinical technical courses. The specific objectives of the intervention are as follows:

- To improve students' OSCE scores in clinical technical skills.
- To increase students' learning motivation.
- To enhance students' self-efficacy.

3. Literature Review

(1). Observational Learning

Observational learning, sometimes referred to as modeling or social learning, is a process by which individuals acquire knowledge and skills through observing and imitating the behaviors of others. During this process, reinforcement, punishment, or conditional control can lead to behavioral changes, whether the observation occurs intentionally or incidentally. Within observational learning, coding and rehearsal are essential concepts. Coding involves transforming observed behaviors into internal representations that can be stored and later reproduced, while rehearsal refers to the practice of these internalized behaviors. Particularly, symbolic coding—in which observed behaviors are encoded using numbers or letters and immediately rehearsed—has been shown to yield the most effective results. Coding without symbolic rehearsal, or symbolic rehearsal without coding, is insufficient to achieve optimal learning outcomes.

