4.2. Student Assessment and Evaluation Tools

Student performance will be assessed using the following tools:

Skills Examinations: Practical OSCEs evaluating core clinical skills.

Written Examinations: Theoretical assessments through multiple-choice and short-answer questions.

Quizzes: Short tests to reinforce knowledge and monitor progress.

Independent Practice Participation: Records of students' engagement in self-directed practice sessions.

5. Research Participants and Setting

This study will be conducted in the Clinical Nursing Skills courses for second- and third-year undergraduate nursing students in the 2024–2025 academic year. The study population will include approximately 170 students (about 85 students per year, with possible attrition due to withdrawal or leave of absence).

Before class, students will engage in pre-class learning through the Moodle system, which includes theoretical principles of nursing skills and instructor-produced instructional videos, supplemented by a technical procedures manual. In the practical sessions, the SimCapture simulation-based training platform will be introduced to support course integration, management, and evaluation in a cloud-based format, thereby facilitating effective post-class learning.

All participants must complete a video-recording consent form prior to participation. Students who decline recording will be excluded from the study and will not be provided with an account or password. Video recordings will capture only hand movements to minimize facial identification. Each student will receive a unique account and password, and students will only have access to their own group's videos.

6. Research Methods and Instruments

This study will adopt an Action Research approach. Action research is a methodology designed to improve practice and address real-world problems, commonly applied in fields such as education, social sciences, and healthcare. It involves iterative cycles of problem identification and planning, action implementation, observation and reflection, and revision and re-planning. A defining feature of action research is its emphasis on practical change, participatory collaboration, and reflective practice. The implementation steps of this study are as follows:

(1) Planning the Intervention

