The research theme is defined as “designing nursing procedural instruction based on observational learning theory.” The intervention plan will be grounded in relevant literature on symbolically coded procedural steps, enhancement of learning motivation, and reinforcement of self-efficacy.

(2) Executing the Intervention

The SimCapture teaching management platform will serve as the central tool for course delivery. This cloud-based system captures audio, video, annotations, and various types of data to facilitate effective training management, documentation, and evaluation. In this study, SimCapture will be applied in the following ways: Each faculty member and student will be provided with a personal account, and the platform will group participants accordingly.

Faculty will develop digital assessment and evaluation tools for each nursing skill. During in-class rehearsal, instructors will annotate student performance using tablets on the cloud system, while students will record their own procedures on mobile devices and upload them to the cloud platform. Students will be able to view their group members' videos, along with instructor feedback, to learn from peers' strengths and correct errors, thereby improving learning outcomes. The platform will be accessible both in the simulation laboratory and remotely, enabling students to review, practice, and participate in asynchronous discussions without time or location restrictions. Students can document their learning progress, which enhances motivation, self-efficacy, and confidence in skill mastery. Faculty will be able to monitor student learning, respond to questions, and review learning histories to design individualized or remedial instructional plans.

(3) Monitoring the Intervention (Data Collection and Feedback)

Throughout the intervention, feedback data will be continuously collected (Table 3), including:

- Student learning portfolios
- SimCapture backend learning records
- Self-efficacy questionnaires
- Learning motivation questionnaires

These data will serve as the basis for reflection and revision of the action plan.

Additionally, trained teaching assistants (TAs) and part-time assistants will serve as observers to support the teaching process and document observations.

(4) Data Analysis, Reflection, and Adjustment of the Action Plan

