Students' technical performance will be assessed using OSCEs, administered twice per semester (midterm and final). Each OSCE will cover nursing skills taught during the course. The OSCE blueprint includes examinee guidelines, standardized patient instructions, examiner guidelines, scoring criteria, evaluation forms, equipment lists, and a demonstration video. The scoring rubric evaluates preparation, procedural performance, communication and caring expressions, health education content, and overall logical flow of operations. Exam content will be determined by the Clinical Nursing Skills teaching committee and validated by five clinical nursing experts and faculty members prior to implementation.

8. Data Analysis

(1) Quantitative Data

Questionnaire data will first be organized in Excel, and the accuracy of data entry will be verified. Preliminary descriptive statistics will be conducted using SPSS, followed by appropriate statistical analyses according to the nature of each research question. A significance level of $p < 0.05$ will be adopted to determine statistical significance. The corresponding research questions and statistical methods are summarized in Table 6.

Correspondence Between Research Questions and Statistical Methods

Research Question	Statistical Method
What are the differences in self-efficacy, learning motivation, and OSCE performance between the two groups at the first measurement?	Independent samples t -test
What are the trends in changes in self-efficacy between the two groups?	Generalized Estimating Equations (GEE)
What are the pre- and post-test changes in learning motivation and OSCE scores within each group?	Paired samples t -test
What are the post-test differences in learning motivation and OSCE scores between the two groups?	Independent samples t -test

(2) Qualitative Data

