Qualitative data will be analyzed using content analysis. Learning portfolio records will be systematically coded and categorized, with each entry labeled by collection date and source (e.g., file, questionnaire, observation, or reflection). Students will be assigned identification codes in the format *S-n-*****. The principal investigator will first classify and organize the collected data, then repeatedly review and integrate the categorized materials. Data will be refined and regrouped into appropriate categories, with iterative reading and reclassification until the categories adequately represent distinct characteristics. This cyclical process ensures analytic rigor and reliability. To protect participants' rights, identifiable student learning records will not be directly presented, and particular care will be taken to avoid any breach of confidentiality or learning equity.

8. Ethical Considerations

Prior to study implementation, the research protocol will be submitted to and approved by the Institutional Review Board (IRB) of the study site. All data will be de-identified before analysis. Before participation, students will be fully informed of the purpose of the study and the evaluation procedures. They will be explicitly advised that participation is entirely voluntary, that they retain the absolute right to refuse to answer any question, and that they may withdraw from the study at any time without providing a reason. Students who withdraw will still complete written examinations, OSCEs, coursework, and self-directed learning sign-in records and will remain eligible to receive course credits. Students who agree to participate will be asked to provide written informed consent. All questionnaires will be collected

anonymously. Interview data will be kept strictly confidential, and all collected data will be coded to ensure participants' names are not disclosed. Hard-copy data will be stored in locked cabinets, while electronic data will be password-protected to prevent unauthorized access.

Reference

1. Lee K-C, Ho C-H, Yu C-C, Chao Y-F. The development of a six-station OSCE for evaluating the clinical competency of the student nurses before graduation: A validity and reliability analysis. *Nurse education today*. 2020;84:104247.
3. Lee K-C, Yu C-C, Hsieh P-L, Li C-c, Chao Y-FC. Situated teaching improves empathy learning of the students in a BSN program: A quasi-experimental study. *Nurse Education Today*. 2018;64:138-143.

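### The between-group comparison of learning motivation is an unadjusted post-test t-test that makes no use of the pre-test; one prespecified baseline-adjusted comparison with a change-based sensitivity analysis would be a cheap improvement.

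*Protocol*

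**What the plan says.** Section 2 of the protocol lists three objectives, one of which is "To increase students' learning motivation". In section 8 (Data Analysis), the table that pairs research questions with methods gives motivation three tests:

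- "What are the differences in self-efficacy, learning motivation, and OSCE performance between the two groups at the first measurement": independent samples t-test.
- "What are the pre- and post-test changes in learning motivation and OSCE scores within each group": paired samples t-test.
- "What are the post-test differences in learning motivation and OSCE scores between the two groups": independent samples t-test, with no covariate.

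A longitudinal between-group model, GEE, is assigned only to "What are the trends in changes in self-efficacy between the two groups".

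The protocol does not say who the two groups are and describes no random allocation. Section 5 expects "approximately 170 students (about 85 students per year", and year is the only evident two-way split of the participants. Under Executing the Intervention, section 6 states "Each faculty member and student will be provided with a personal account", which suggests that both years use SimCapture. Under Ethical Considerations the protocol says "All questionnaires will be collected", and after a page break the sentence goes on to say that this is done anonymously. The same section says that collected data will be coded.

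**The concern.** Motivation is measured before and after, but the between-group comparison at the end uses the second measurement alone. In randomised groups this would cost only precision. Here no randomisation is described, and if the groups are different study years there is no reason to presume that they start level. A post-test difference would then mix whatever gap existed at the pre-test with whatever arose during the course.

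The other two rows do not fill the gap. Paired tests within each group show whether each group moved; a significant change in one and a non-significant change in the other is not a test of a difference between them. The first-measurement t-test is a weak safeguard, and the table attaches no consequence to its result. What is at stake is how a between-group result on one of the three objectives would be read.

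**Working it through.** The protocol gives no sample size calculation, SD, effect size or pre-post correlation for motivation, so there is no figure to reproduce. What follows is an illustration.

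**Inputs.** Assumed: n = 85 per group (section 5 gives about 85 per year, but the groups are undefined); independent students; equal SDs, set to 1; pre-post correlation r = 0.3, 0.5, 0.7; baseline gap g = 0.3 SD. The 0.05 level is from section 8; two-sided testing is assumed.

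**1. Balanced baselines: half-width of the 95% CI.**
- t-test: t(168) × √(2/85) = 1.974 × 0.1534 = 0.303 SD.
- ANCOVA: t(167) × √((1 − r²) × 2/85) = 0.289, 0.262, 0.216 SD.
- Ratios 0.954, 0.866, 0.714: the interval is 5%, 13% and 29% narrower.

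**2. Baseline gap, no group effect.** Let k be the share of the gap that would persist to the post-test anyway. The bias is k × g for the t-test, (k − r) × g for ANCOVA and (k − 1) × g for the change score. Standard errors are √(2/85) for the t-test, √((1 − r²) × (2/85) × (1 + g² × 42.5/168)) for ANCOVA and √(2(1 − r) × 2/85) for the change score. The noncentral t distribution then gives these rejection rates, shown for r = 0.3 / 0.5 / 0.7:

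| What happens to the gap | t-test | ANCOVA | Change score |
|---|---|---|---|
| Regression to a common mean (k = r) | 9 / 16 / 28% | 5% | 21 / 16 / 12% |
| Persists in full (k = 1) | 49% | 29 / 20 / 13% | 5% |
| Transient (k = 0) | 5% | 9 / 20 / 47% | 38 / 49 / 71% |

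The matching t-test biases are 0.09 / 0.15 / 0.21 SD (k = r), 0.30 SD (k = 1) and 0 (k = 0). For ANCOVA they are 0, then 0.21 / 0.15 / 0.09 SD, then −0.09 / −0.15 / −0.21 SD.

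**3. Where the ranking turns.** ANCOVA is less biased than the t-test when |k − r| < k, that is k > r/2: more than 15%, 25% or 35% of the gap must persist. It is less biased than the change score when k < (1 + r)/2: below 65%, 75% or 85%.

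**4. The first-measurement test as a safeguard.** With 85 per group, a t-test detects a true 0.3 SD gap with power of about 49%. A non-significant result there would not justify leaving the pre-test out.

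**The case against.** The row asks about post-test differences and names a test of post-test differences; it is not wrong as worded. Nothing in section 8 calls the result an intervention effect, and the rejection rates above are errors only if it is read as one. The paired tests do address whether motivation rose, though without a control for time. All of that stands.

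A reader might infer that the t-test is invalid, or that ANCOVA is shown to be better. The protocol supports neither. The gap, SD, correlation and group size are all assumed, no text indicates that a gap exists or how it would evolve, and with a transient gap the planned test is the better one.

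Independence is also assumed, while section 4.1 describes small-group teaching by nine faculty members. If clusters held about 85/9 = 9.4 students with an intraclass correlation of 0.02 to 0.10 (both assumed), standard errors would grow by a factor of √(1 + 8.4 × ICC), or 8 to 36%. The figures are therefore more precise than the design allows.

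The undefined groups are the larger problem: if both groups use SimCapture, adjustment only refines a year-against-year comparison. This too stands, and it is why defining the groups comes first in the fix.

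Three further inferences should be resisted. The pre-test is not absent from every between-group contrast, since the first-measurement row is one. The timing of the pre-test cannot be called unstated, because section 6 refers data collection to a Table 3 that is not in the text available. Anonymous collection need not rule out linkage, because coding of the data is also mentioned.

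**Conclusion.** The point holds as a cheap improvement, not as an error that invalidates the plan. The protocol itself fixes the method, so this is not a detail left to an SAP. In groups with no described randomisation, a collected pre-test enters neither the between-group post-test comparison nor any between-group comparison of change.

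Under the stated assumptions the gain ranges from a 5% narrower interval to avoiding a rejection rate of up to 49% when there is no effect. The same adjustment can do harm if the baseline gap is transient (up to 47%, against 5% for the planned test). That reversal is the reason to pair one named main analysis with a sensitivity analysis resting on a different assumption. No adjustment turns the contrast into an intervention effect if both groups are exposed.

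**What to change.** 1. State who the two groups are and whether each uses SimCapture. If both do, say that the contrast is not an intervention effect, with or without adjustment.
2. For motivation, replace the post-test t-test with ANCOVA of the post-score on group and pre-score, reporting the adjusted difference with its 95% CI.
3. Name a change-score or GEE group-by-time analysis as sensitivity. If the two disagree, report that the conclusion depends on the assumption made about the baseline gap.
4. Treat the within-group paired tests as descriptive for the between-group question.
5. Make explicit that pre- and post-questionnaires are linked by a code, and reconcile this with the statement on anonymous collection. The planned paired tests already need the link.
6. Do not carry the adjustment over to OSCE with the midterm score as a pre-exposure baseline: section 7 describes only midterm and final OSCEs, so the midterm may follow the start of exposure.

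Cost: the shared motivation and OSCE row has to be split and one sensitivity analysis added. No new measurement is needed, and SPSS, which the protocol already names, fits both models. The linkage wording may touch the collection procedure and the participant information. The remaining downsides are little gain if the pre-post correlation is low, and bias from ANCOVA if the baseline gap is transient.
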